5.2.2 Surgery - Minimally Invasive Scaling and Root Planing and Emdogain® First Application

Patients that have been randomized and have scaling and root planing with Emdogain® treatment during Visit 2 are considered enrolled in the study. Each subject will receive local anesthetic and be treated in one visit with a sequence of steps defined by the treatment assignment:

- Test treatment: For the quadrant assigned to scaling and root planing + Emdogain® the following steps should be conducted for treatment: scaling and root planing, control of bleeding, application of PrefGel® (until there is clear overflow from the pocket) to remove any residual smear layer for 2 minutes, irrigation with sterile saline thoroughly, and application of Emdogain® starting apically and advancing coronally until there is clear overflow from the pocket.

- Control treatment: For the contralateral quadrant, assigned to scaling and root planing alone, the following steps should be conducted at the same visit as the test treatment: scaling and root planing and control of bleeding.

Mechanical debridement will be carried out in the manner commonly performed by the clinician (e.g., hand instrumentation, ultrasonic scalers with diamond tips). No antimicrobial agents or techniques (antibiotics or antiseptics, photodynamic therapy) will be applied during treatment. No vasoconstrictors (other than 1:100 000 or 1:200 000 epi in local anesthetic) or hemostatic agents will be used in surrounding soft tissues or pockets. Bleeding will be stopped by conventional techniques as much as possible. No sutures or periodontal dressings will be applied.

In order to standardize treatment across centers, only loupes or a microscope can be used as an assistive visual aid for debridement and removal of calculus from defects.

Other quadrants not being evaluated in the study should be treated according to standard practice.

5.2.3 Plaque Removal and Emdogain® Second Application

After the surgery, all subjects will be given a periodontal cleaning with supragingival plaque removal for both the test and control quadrants at Visit 3. At this visit, Emdogain® will be re-applied to the test quadrant. In detail, this procedure involves no anesthesia, supragingival plaque removal at low power setting, no Prefgel® application, and application of Emdogain® will start apically and advance coronally (as appropriate for treatment assignment group).

Other quadrants not being evaluated in the study should be treated according to standard practice.

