3.1 Type and Design of Study

This study is a post-market, prospective, split-mouth, controlled, multi-center study. Split-mouth design: each patient receives two treatments that are randomly assigned to either the right or left quadrant of the maxillary or mandibular arches.

- *Test Treatment:* Minimally Invasive Scaling and Root Planing (SRP) and applications of Emdogain®
- *Control Treatment:* Minimally Invasive Scaling and Root Planing (SRP) alone

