4.6 Risk Analysis, Risk/Benefits

The device risk analysis and risk assessment for Emdogain® and PrefGel® was conducted according to EN ISO 14971, part of the Straumann risk management process which ensures adequate handling of risk analysis, risk evaluation, risk control and evaluation of overall residual risk acceptability. Full results are included in the Risk Management Report for Emdogain®, PrefGel® and Osteogain Version 1.0 dated 1 September 2014. Refer to the Section 7.2.6 of this protocol for a description of the anticipated adverse device effects.

Read carefully the risks associated with the investigational device and the procedures involved in its use listed in Instructions For Use in Appendix 1 and Appendix 2 under Warning and Cautions/ Precautions.

An anticipated benefit of the application of Emdogain® in combination with the minimally invasive surgical technique is the decrease of pain at treatment until 2 weeks after the surgery, as the decrease in root dentin hypersensitivity.

The identified hazards have been mitigated and the overall residual risks for the described medical devices are in the acceptable range.

In conclusion, the risks associated with the use of the Emdogain® and PrefGel® are acceptable when weighed against the benefits to the patient.

5 Study Procedures

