5.2.1 Selection and Assignment of Quadrants

The inclusion and exclusion criteria will be reviewed (Section 3.7.1 and 3.7.2). If the subject remains eligible, randomized treatment assignment of a quadrant (test or control), will be done via randomization envelopes. At Visit 2, the Investigator or designee will open a sealed randomization envelope. The randomization envelope will identify the treatment assignment for the right and left quadrants, both in the same arch of the eligible patient. **Randomization envelopes must be open in sequential order.**

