5.3.7 Root Dentin Hypersensitivity

Presence of root dentin hypersensitivity is examined by isolating the neighboring teeth and using a conventional air blast for three seconds on the study tooth. The root dentin hypersensitivity is recorded as "none" (no reaction from the subject), "mild" (sensible with no pain), "moderate" (sensible with slight pain), or "severe" (sensible with pain that persists for a while). Assessment will be done at Visit 2 – Minimally Invasive Scaling and Root Planing and Emdogain® First Application (SURGERY) and from the 3-month to the last follow-up visit.

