Appendix 3 – Treatment Workflow

Appendix 4 – Visual Analog Scale (VAS)

 CR 01/15	Subject Initials:	

 

	1-2 Days after Treatment
	Subject ID:	

 

 

	
	Date:	

 

 

 

 

 

	

Instructions:
 To be completed by the patient
 Complete this page 1 to 2 days after treatment.
 Indicate the level of pain in the area of your mouth treated for the study.
 Please mark the lines as instructed below.

RIGHT side of mouth

Please mark your pain level by drawing one vertical mark | through the line below.

No pain

Worst pain possible

LEFT side of mouth

Please mark your pain level by drawing one vertical mark | through the line below.

No pain

Worst pain possible

 CR 01/15	Subject Initials:	

 

	1 Week after Treatment
	Subject ID:	

 

	

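### No patient masking or matching control-side step is described, so the pain comparison, and in part the hypersensitivity comparison, is open to expectation bias of unknown size

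*Combined protocol and SAP*

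**What the plan says.** **Design and allocation.** Section 3.1 calls the trial neither open-label nor masked: "This study is a post-market, prospective, split-mouth, controlled, multi-center study". Section 5.2.1 says "At Visit 2, the Investigator or designee will open a sealed randomization envelope"; it gives no instruction to keep the result from the patient.

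**Visit 2 (Section 5.2.2).** "Each subject will receive local anesthetic", so the patient is awake. After debridement, the test quadrant receives PrefGel for 2 minutes, saline irrigation and Emdogain to overflow. For the control quadrant, "the following steps should be conducted at the same visit as the test treatment: scaling and root planing and control of bleeding". No vehicle, sham or irrigation is listed there.

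**Visit 3 (Section 5.2.3).** Both quadrants are cleaned, but only the test quadrant receives Emdogain again: "this procedure involves no anesthesia, supragingival plaque removal at low power setting, no Prefgel® application, and application of Emdogain® will start apically and advance coronally".

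**Pain.** Section 5.3.6 has the patient mark a 100 mm scale at home at 1-2 days, 1 week and 2 weeks. Each page of Appendix 4 carries one line for the right side and one for the left, under the instruction "Indicate the level of pain in the area of your mouth treated for the study".

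**Hypersensitivity.** In Section 5.3.7 an air blast is applied to the study tooth and the patient's reaction is recorded in four grades, at Visit 2 and from 3 to 12 months. Section 5.3 says one examiner takes all measurements, without saying whether that examiner is masked.

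**Expectations.** Section 4.6 says that an anticipated benefit of Emdogain "is the decrease of pain at treatment until 2 weeks after the surgery, as the decrease in root dentin hypersensitivity". Section 5.1.1 requires risks, complications and benefits to be explained at consent. Section 7.2.6 lists root sensitivity and pain among the expected adverse events of Emdogain, and short-lived dentin hypersensitivity for PrefGel.

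**Status.** Section 2.2 makes post-surgical pain and root dentin hypersensitivity secondary objectives. Section 3.4.3 plans the comparison of pain between treatments.

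**The concern.** For pain, the patient is the measuring instrument and scores both sides on one page. A patient who knows which side received the gel, and who has been told what it may do, can score the sides apart for that reason alone. Randomizing left and right does not protect against this, because the shift follows the treatment and not the side. Pooling centers does not help either.

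The study aims to assess patient-reported outcomes and to give a first indication for a larger trial (Section 2). A favorable pain result could not be separated from expectation, and the analysis text in Section 8.3 does not mention the problem.

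**Working it through.** There is no figure in the plan to reproduce. Section 8.1 gives 50 subjects and dropout of up to 15%, but no alpha, power, effect or standard deviation. The check is therefore mainly a reading of the order of events.

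**1. What can reveal the side, and when**

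| Event | Timing | Difference between sides |
|---|---|---|
| Visit 2 treatment | Day 0 | PrefGel, irrigation and Emdogain on test side only; awake, local anesthetic |
| Pain mark 1 | 1-2 days | Patient marks right and left |
| Pain mark 2 | 1 week | Patient marks right and left |
| Pain mark 3 | 2 weeks | Patient marks right and left |
| Visit 3 | Day 14-21, window 2-3 days | Emdogain on test side only; no anesthesia |
| Hypersensitivity follow-up | 3, 6, 9, 12 months | Patient reacts, examiner records |

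The earliest Visit 3 is Day 14 − 3 = Day 11, or 14 − 2 = Day 12. The first two pain marks therefore always precede it. The third usually falls at or before it; Section 6.4 also lists pain scale completion at Visit 3, without placing it before or after the gel. For pain, the step that matters is Visit 2. All four follow-up hypersensitivity grades come after Visit 3, so both visits matter there.

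**2. How a reporting shift enters the result**

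Let D be the within-patient difference in pain, δ the true effect, b the shift caused by knowing the side, and σ the standard deviation of D. Then

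- mean of D = δ + b
- standard error of the mean = σ/√n

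The shift b does not depend on n. A larger sample narrows the interval around δ + b, not around δ.

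**3. Illustration only**

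Assumptions that are not in the documents: δ = 0, σ of 15 to 30 mm, b of 3, 5 or 10 mm on the 100 mm scale, and a two-sided 5% paired t-test. Evaluable patients: 50 × 0.85 = 42.5, taken as 42. The rejection rate comes from the noncentral t distribution with n − 1 degrees of freedom and noncentrality b√n/σ. For example, b = 5, σ = 20 and n = 42 give 5 × 6.48/20 = 1.62 and a rejection rate of 35.3%.

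False-positive rate, n = 42:

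| σ (mm) | b = 3 mm | b = 5 mm | b = 10 mm |
|---|---|---|---|
| 15 | 24.4% | 55.9% | 98.8% |
| 20 | 15.8% | 35.3% | 88.6% |
| 25 | 11.8% | 24.4% | 71.6% |
| 30 | 9.7% | 18.4% | 55.9% |

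With n = 50 the ranges over σ rise to 10.7%-28.4%, 21.1%-63.7% and 63.7%-99.6%. By symmetry, a shift of the same size against Emdogain gives the same rates in the other direction.

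**The case against.** The case against has real substance, and most of it limits the point.

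- **Silence is not a declaration.** A reader might infer that patients are openly told their side. The text does not say so. It describes no masking and no sham; the consent pages and the Appendix 3 workflow figure were not available.
- **Visit 3 is not the main route for pain.** A reader might blame the unanesthetized re-application, but at least two of the three pain marks precede it. At Visit 2 the anesthetic may blunt what the patient feels, although it does not hide what the patient sees or hears.
- **Hypersensitivity is not a side-by-side self-report.** The patient reacts and the examiner records, so patient expectation is only one of two routes.
- **Direction.** A reader might infer that bias must favor Emdogain. Section 4.6 points that way, but consent also covers risks, and Section 7.2.6 names pain and root sensitivity as expected adverse events.
- **Size.** A shift of 3 to 10 mm is an assumption, not an estimate. Section 8.3.3 plans only descriptive summaries for pain, so the false-positive rates apply only if a test is added. Without one, the shift still enters the reported difference.
- **Scope.** This is a pilot. The primary endpoint, attachment level, is not a patient report, so this point does not reach it. Pain is missing from the secondary endpoint list in Section 3.4.2, though it is a secondary objective in Section 2.2.

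What the objection does not remove is that a trial run exactly as written treats the two sides visibly differently, takes no described step to conceal this, and then asks the patient to compare them.

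**Conclusion.** The point holds in limited form. No patient masking and no matching control-side step are described, and the Visit 2 procedure can reveal the side before any pain mark is made. The pain comparison is therefore open to expectation bias, more likely in favor of Emdogain but not certainly so. Hypersensitivity is exposed through both the patient and an examiner not stated to be masked, and the Visit 3 re-application adds to this.

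The size cannot be derived from the documents. The rates above show only that, under the stated assumptions, a modest shift could produce an apparent pain difference. The conclusion rests on the supplied text being complete on masking.

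**What to change.** **For any patient still to be treated.** State in Sections 5.2.1 to 5.2.3 that the patient is not told which quadrant receives Emdogain, and that the envelope and syringes are kept out of view. At Visits 2 and 3, have the operator repeat the application motions at the control quadrant with nothing delivered, so the control treatment is unchanged. Acknowledge that masking will be imperfect, especially at Visit 3, where the patient may feel or taste the gel. State also whether the examiner recording hypersensitivity knows the side.

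**Check on masking.** A question on which side the patient believes was treated may be added and reported descriptively. Do not stratify the pain difference by the answer: patients may infer the side from the pain itself, so a true effect would also produce a larger difference among correct guessers.

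**For patients already treated.** Report pain and hypersensitivity as unmasked, exploratory comparisons and base no benefit claim on them. This may be the only step left. The Synopsis planned enrollment through December 2016 and follow-up to December 2017, while the protocol is Version 5.0 of 29 March 2018. The recruitment in Germany mentioned in Section 3.7, which the Synopsis country list omits, leaves the actual status uncertain.

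**Cost.** The labelling is a sentence in the analysis plan and report. If enrollment is open, add a few minutes at two visits, amendment and consent wording, and one question on an existing form. No extra visits, staff or patients are needed.

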5.2.4 Post Treatment Instructions

After both procedures described above, at Visit 2 and 3, the subject will be sent home with post-treatment instructions that includes the use of antiseptic oral rinse (e.g., 0.12% chlorhexidine solution) for one week with no brushing during that time. The subject will also be instructed to refrain from flossing or using a waterpik for one month after the treatment. No local or systemic antibiotics should be prescribed. When brushing, soft brushes are recommended to be used on a 90° angle on the tooth surfaces in order to avoid sulcular brushing.

5.2.5 Supragingival Prophylaxis

Supragingival Prophylaxis includes plaque control and supra-gingival teeth cleaning, with no subgingival instrumentation.

5.2.6 Regular Periodontal Maintenance

At each follow-up visit, regular periodontal maintenance will be provided and may include plaque control, supra-gingival teeth cleaning, or any other necessary therapy that is standard practice at the study center.

5.3 Outcome Assessments

The following measurements will be taken by the same examiner throughout the study.

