5.3.1 Pocket Probing Depth (PPD)

Probing Pocket Depth (PPD) will be measured by recording the distance from the gingival margin to the bottom of the probable pocket at 6 sites (mesiofacial, facial, distofacial, distolingual, lingual, mesiolingual) on the teeth in the contralateral quadrants.

Assessment will be done at screening/baseline visit and from the 3-month to the last follow-up visit.

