5.3.2 Gingival Margin (GM)

The Gingival Margin (GM) measurements will be performed simultaneously with the PPD measurements. GM will be measured by recording the distance from the Cemento-Enamel Junction (CEJ) to the margin of the gingiva at 6 sites (mesiofacial, facial, distofacial, distolingual, lingual, mesiolingual) on the teeth in the contralateral quadrants.

In periodontal sites with a visible CEJ (see Figure 2), the distance from the CEJ to the margin of the gingiva will be measured as noted in the diagram below.

In periodontal sites with no visible CEJ (see Figure 3), the periodontal probe will be inserted into the periodontal pocket and angulated approximately 45° in order to manually detect the reference line. The depth of insertion into the periodontal pocket will be recorded as the GM.

A negative value for the GM indicates gingival recession. A positive value for the GM indicates the gingiva is covering the CEJ. A zero indicates the gingiva is at the same level as the CEJ.

Assessment will be done at screening/baseline visit and from the 3-month to the last follow-up visit

[figure not shown]

Figure 2: Measurement of the GM when the CEJ is visible.

[figure not shown]

Figure 3: Measurement of the GM when the CEJ is not visible

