5.3.3 Clinical Attachment Level (CAL)

Clinical Attachment Level (CAL) measurements will be derived from the PPD and GM measurements as follows:

$$\text{CAL} = \text{PPD} - \text{GM}$$

Measurement will be calculated from the PPD and GM values taken at screening/baseline visit and from the 3-month to the last follow-up visit.

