7.3.6 Additional Safety Reporting

Straumann will report additional safety information to the centers that is relevant to the protocol or study device and may affect the risk/benefit ratio, the rights, safety or welfare of subjects, or the integrity of the study. Such reports may include notification of any changes to the Instructions for Use, any publications or interim reports, or any product recalls.

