8.3.3 Interim Analysis of Endpoints

Interim analysis will be performed for all above endpoints between the surgery and 3 months post-surgery. Optional interim analyses will be performed at 6 months and 9 months post-surgery, as applicable.

In addition, the seven-point scales (mean, standard deviation, minimum, 25% percentile, median, 75% percentile and maximum) of the change in pain for each treatment group will be presented at 1-2 days, 1 week and 2 weeks after surgery.

9 Data Management

The general data management procedures are described below, details can be found in the separate Data Management Plan (DMP).

Required clinical data for this study will be collected and recorded in the clinical database using a paper Case Report Form (CRF) for all study subjects from whom informed consent is obtained. Site numbers and subject numbers will be used to track subject information throughout the registry. The Principal Investigator or authorized designee is responsible for the timely completion and signature of all CRFs.

All original CRFs will be retrieved from the site by the study monitor and sent to the data management. Double data entry and computer programmed error checks will be carried out by data management personnel for inconsistent, illogical and/or missing data. If validation of data leads to discrepancies, data management will generate queries. The timely resolution of the queries is under the responsibility of the monitor and the Investigators at site. The query process is an ongoing process starting with the first data entered into the database.

The electronic clinical database used for this study has a security system that prevents unauthorized access to the data and any deletion of data (audit and edit trail). All above mentioned tasks will be carried out according to Straumann Standard Operating Procedures, Protocol Version 5.0, 29-Mar-2018

except for those tasks performed by Straumann contracted Contract Research Organizations (CRO), where the CRO procedures shall be used.

10 Obligations of the Principal Investigator

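### The constant examiner is not masked to the treated side or to earlier charting, and site access to by-treatment interim results is not restricted, so 12-month CAL is open to expectation bias of unknown size

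*Combined protocol and SAP*

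**What the plan says.** Section 3.1 labels the design without any masking term: "This study is a post-market, prospective, split-mouth, controlled, multi-center study". Section 5.3 opens with "The following measurements will be taken by the same examiner throughout the study" and adds no condition on what the examiner may know.

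Allocation is disclosed at surgery. Section 5.2.1: "At Visit 2, the Investigator or designee will open a sealed randomization envelope". The envelope names the treatment for the right and left quadrants. Under sections 3.3, 5.2.2 and 5.2.3 only the test quadrant receives PrefGel and Emdogain, with Emdogain repeated at Visit 3. The control quadrant has no sham step.

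PPD is read at six sites per tooth "on the teeth in the contralateral quadrants" (5.3.1). On the primary endpoint, 5.3.3 says "Clinical Attachment Level (CAL) measurements will be derived from the PPD and GM measurements as follows", namely PPD minus GM. Where the CEJ is not visible, 5.3.2 has the probe "angulated approximately 45° in order to manually detect the reference line".

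On interim looks, 8.3.3 says "Interim analysis will be performed for all above endpoints between the surgery and 3 months post-surgery", with optional looks at 6 and 9 months. Section 8.3.1 summarises the change in CAL by treatment group. Section 7.3.6, a safety-communication clause, lists "any publications or interim reports" among the things the sponsor may send to centers.

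**The concern.** CAL, PPD, GM and BoP all depend on one person's readings at the chair, and part of the GM reading is a matter of judgement. If that person knows or remembers which side was treated, expectation can enter the readings. A split-mouth design removes between-patient differences, but it does not remove this: the same person reads both sides, so a side-specific tendency goes straight into the test-minus-control difference.

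Change from baseline does not remove it either. Baseline PPD and GM are charted at Visit 1 and the envelope is opened at Visit 2, so only the follow-up readings are exposed.

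There are two further channels. Sight of earlier charts can anchor a reading to the previous value on each side. And if by-treatment CAL results at 3 months reach site staff, they may set expectations for 12-month visits still to come. At stake is the 12-month CAL contrast, which section 2 treats as a first indication on which a larger trial would be based.

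**Working it through.** **Step 1. Is masking covered anywhere?** The safeguards in the protocol are:
- sealed envelopes opened in sequence (5.2.1), which protect assignment;
- one constant examiner (5.3), which protects consistency over time;
- standardized procedures and investigator training (8.3), which support pooling across centers.

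None concerns what the examiner knows when measuring. No section separates examiner from operator or says who may see interim results.

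**Step 2. When could the examiner learn the side?** The same-examiner rule covers all of 5.3, so the examiner has work on both treatment days: root dentin hypersensitivity at Visit 2 (5.3.7) and the plaque score at Visit 3 (5.3.5). In section 6.3 the hypersensitivity reading is listed after quadrant identification and treatment assignment but before randomization, so the order relative to opening the envelope is not settled. Keeping the envelope and notes away is therefore not enough by itself; these two visits also need an order of events.

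**Step 3. Size of a possible shift (assumed inputs).** The documents give neither the probe resolution nor any measure of examiner bias. Assume that a share *p* of test sites is read *d* mm more favourably at follow-up, with control sites unaffected. Then shift = *p* × *d*.

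| | d = 0.5 mm | d = 1 mm |
|---|---|---|
| p = 10% | 0.05 mm | 0.10 mm |
| p = 30% | 0.15 mm | 0.30 mm |

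For scale, the full-group split-mouth rows of the table in Appendix 1 show attachment-gain differences of 0.3, 0.6, 0.6 and 0.5 mm. A deep-pocket subgroup shows 1.3 mm.

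**Step 4. Against the study's precision.** Section 8.1 gives 50 subjects and up to 15% dropout: 50 × 0.85 = 42.5, so about 42 evaluable. No SD, effect size, alpha or power is stated, so 50 cannot be derived. Assume an SD of the within-subject difference of 0.8-1.5 mm. The 95% CI half-width is *t*(0.975, 41) × SD / √42:
- SD 0.8: 2.02 × 0.8 / 6.48 = 0.25 mm
- SD 1.5: 2.02 × 1.5 / 6.48 = 0.47 mm

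Chance that a 95% CI for the paired difference excludes zero when there is no true effect (noncentral *t*, n = 42):

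| Shift | SD 0.8 | SD 1.0 | SD 1.3 | SD 1.5 |
|---|---|---|---|---|
| 0 | 5% | 5% | 5% | 5% |
| 0.05 mm | 7% | 6% | 6% | 6% |
| 0.10 mm | 12% | 10% | 8% | 7% |
| 0.15 mm | 22% | 16% | 11% | 10% |
| 0.30 mm | 66% | 48% | 31% | 24% |

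The planned analysis of the primary endpoint is descriptive. The table shows only how such a shift would move an estimate and its interval.

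**Step 5. Could interim results matter in time?** The synopsis has initiation in September 2015 and enrollment through December 2016, i.e. 16 months. Assume uniform accrual and an interim run after the last subject's 3-month visit (month 16 + 3 = 19). Subjects enrolled by month 19 − 12 = 7 have finished, so 9/16 = 56% (28 of 50) still have the 12-month visit ahead. With a 3-month reporting lag (month 22) it is 6/16 = 38% (19 of 50). The protocol does not define the interim trigger, so these figures rest on that assumption.

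**The case against.** **The stated purpose limits the consequence.** Section 8.1 calls this a pilot to create a workflow, and 8.3.1 plans only descriptive statistics for the primary endpoint. That stands. It lowers the cost of a biased estimate, but the estimate still informs the next trial.

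**Section 7.3.6 is a safety clause.** A reader might infer that the sponsor plans to circulate efficacy tables to sites. The text does not support that: interim reports appear beside changes to the instructions for use and recalls, as safety-relevant information, and 8.3.3 describes no distribution to sites. The supported statement is that access is unrestricted and that sending interim reports is permitted.

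**The examiner may not know the side.** A reader might infer that the examiner is the operator or opens the envelope. The documents do not say so; they only fail to prevent it.

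**Masking may not be available everywhere.** A reader might infer that every site can mask its examiner with existing staff, or that the gel leaves nothing visible at follow-up. Neither is documented. References to a designee (5.2.1), a delegation log (7.2) and site personnel (11.3.2) suggest more than one person per site, but there is no roster.

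**A masked-versus-unmasked comparison would say little.** With 4 centers and one examiner held constant at each, that split would largely coincide with center. This stands, so it belongs in a descriptive listing only.

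**It may be too late.** The text in section 9 carries Version 5.0, 29-Mar-2018, while the synopsis plans follow-up complete by December 2017. If that plan held, only disclosure is left.

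**The detailed SAP** announced in section 8 is not in the text available. It could address access to results, but the protocol does not refer to it for masking.

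**Conclusion.** The gap is real and stands as a risk. The examiner is required to be constant but is not masked to side or to earlier charting, and nothing restricts site access to by-treatment interim CAL. The 12-month CAL, PPD, GM and BoP readings are therefore open to expectation bias that neither the split-mouth design nor change from baseline removes.

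The documents do not show that bias occurred, and its size is unknown. The 0.05-0.3 mm range rests on assumed shares of sites, assumed reading steps and an assumed single direction. At the lower end it would be negligible. At the upper end it would be similar to the CI half-width (0.25-0.47 mm under the assumed SDs) and equal to the smallest full-group split-mouth difference in Appendix 1. The chart separation and the interim restriction are worth making because they need no added staff, not because a large bias has been established.

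**What to change.** **In 5.3:**
- Envelope contents and treatment notes are kept apart from the charting form, and each visit is charted without sight of earlier values.
- Where the site's examiner is not the operator, the examiner is not told the side, takes the Visit 2 hypersensitivity reading before the envelope is opened and the Visit 3 plaque score before the gel is re-applied, and is absent during application. The same-examiner rule stays.
- Where examiner and operator are the same person, record this on the CRF and report it as a limitation. Show any masked/unmasked split descriptively.

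**In 8.3.3:** by-treatment interim efficacy results are not released to site staff before the last 12-month visit, with an exception for safety information under 7.3.6.

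**Cost:** protocol wording, a separate charting form and one CRF item. Any 3-month publication waits. Sites where one person operates and examines gain only the chart separation, the interim restriction and the disclosure.

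**If follow-up visits are already complete:** document for each site who knew the allocation and who saw interim results, and report it with the 12-month CAL contrast.
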